Choice of eGFR threshold (45mL/min/1.73m²) in study: Metformin is commonly used safely in patients with moderate chronic renal impairment. In one example in Tayside,⁵⁴ 4.8% of patients on metformin in Tayside had a serum creatinine >150umol/L with one case of lactic acidosis in 4600 patient years; that case was related to acute myocardial infarction with secondary acute renal failure and not due to metformin therapy. In another study from Edinburgh,⁵⁵ researchers concluded that an eGFR threshold between 36 – 40mL/min/1.73m² would be useful and safe. The UK National Institute for Clinical Excellence published criteria for use of metformin in chronic renal impairment in 2008.⁵⁶ This guidance states that metformin is contraindicated with a serum creatinine >150 micromol/L or eGFR <30 ml/minute/1.73 m². Furthermore the guideline recommends that the dose of metformin be reviewed if the serum creatinine exceeds 130 micromol/L or the eGFR is below 45 ml/minute/1.73 m².

Accordingly, we have selected a baseline eGFR threshold of 45mL/min/1.73m² in this study below which participants will not be recruited. If during participation a subject's eGFR falls to <45mL/min/1.73 m² consideration will be given to IMP dose reduction. If during participation a subject's eGFR falls to <30mL/min/1.73 m² IMP will be discontinued.

Side effects. Please refer also to the SmPC.⁵³

- Very rare (<1/10 000): Chest discomfort, palpitation. These should only be recorded as AEs if associated with an SAE, or if they result in discontinuation of study medication or dose reduction.

- Common (>1/100): taste disturbance, abnormal stools, hypoglycaemia (see below), myalgia, lightheadedness, dyspnoea, nail disorder, rash, sweating increased, chills, flu syndrome, flushing, skin reactions. These should only be recorded as AEs if they result in discontinuation of study medication or dose reduction.

- Common (> 1/100): Decreased vitamin B12 absorption has been reported in long term use, however although plasma levels fell significantly in the HOME trial over 4.3 years,¹⁷ actual levels usually remained within standard reference ranges. Vitamin B12 Serum levels falling below the local assay reference range (150 pmol/L or equivalent) should be recorded as AEs.

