- Very common (>1/10): Gastrointestinal effects are most common and may include nausea, vomiting, diarrhoea, abdominal discomfort, headache and loss of appetite. It is well recognised that these side-effects usually resolve spontaneously following initiation of therapy and are minimised if the dose is titrated upwards (as will be done in the study). These events should only be recorded as AEs if they result in discontinuation of study medication or treatment dose reduction.

Serious Adverse Reactions that are expected (<0.5%)

- Lactic acidosis may occur extremely rarely (see page 28 above). It will usually be associated with hospitalisation and reported as an SAE.

Abnormal Laboratory Findings

The following will be specifically recorded as AEs on CRF pages:

- LFTs: any abnormal results of >2.5 times upper limit of normal
- Reduction in eGFR to < 45 ml/min/1.73 m² and < 30 ml/min/1.73 m²
- Hb < 10.0 g/dL AND fall of >1.5 g/dL from baseline
- MCV > 105 fL

Other. Participants will be advised to avoid alcohol excess during the study though this is not an exclusion criteria. Their primary care physician (where applicable) will be

advised that if commencing a medication which may lead to a deterioration in renal function, such as NSAIDs, they should monitor renal function and advise the study doctor of any deterioration.

Interruption of treatment: in preference to permanent treatment withdrawal or withdrawal from the study, investigators will permit treatment interruption of any duration (which will be documented) in any participant who develops any of the following:

- Acute illness: severe infection, shock, acute or clinically unstable cardiac failure
- Acute myocardial infarction or other acute coronary syndrome
- Surgery: treatment will be discontinued 48 hours prior to elective surgery with general anaesthesia and will be recommenced no earlier than 48 hours following surgery and only when it has been confirmed that renal function has returned to pre-operative levels.
- Requirement for investigation involving intravascular iodine-containing contrast agent (as per national guidelines): treatment will be discontinued 48 hours prior to investigation and recommenced no earlier than 48 hours afterwards.
- Anaemia (Hb<10.0 g/dL AND fall of >1.5 g/dL from baseline) considered by the local investigator to be potentially related to study medication.

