In these cases, treatment will be restarted where possible in accordance with the Investigator's clinical judgement, local practice, standard-of-care, and national guidelines (renewed titration from a lower starting dose is not usually required unless interruption has been prolonged e.g. more than four weeks). Where treatment interruption has persisted for four weeks or more it will be documented as permanent.

Withdrawal of treatment: Investigators will withdraw from treatment any participant who develops any of the following:

- Pregnancy: discontinue if participant becomes, or intends to become, pregnant
- Development of new contraindications to metformin
 - o hepatic impairment (ALT > 3.0 ULN)
 - o renal impairment with eGFR <30 mL/min/1.73m² during study – see page 28
- Biochemically-confirmed severe lactic acidosis (>5.0 mmol/L with acidosis)
- Hypersensitivity to metformin

Dose reduction of treatment: Where eGFR falls below 45 ml/min/ 1.73m² on any measurement Investigators should permanently reduce metformin dose to 500 mg twice daily.

Withdrawal from study: Investigators will withdraw from the study any randomized participants with:

[figure not shown]
- confirmed pregnancy
- withdrawal of consent for follow-up
- any other reason agreed between the participant and the site Principal Investigator

At the end of the study: No further study medication will be provided.

Assessment of adherence: Tablet counts will be carried out by study nurses following at relevant study visits, including the final clinic visit, to assess adherence. This will be documented in the eCRF. Site medical and nursing staff will also discuss and reinforce adherence to study medication with participants.

Concomitant medication. No concomitant medication is specifically excluded.

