2.4.5.4. EVENTS OF PARTICULAR INTEREST

Events of particular interest have been defined as:

- Lactic acidosis
- ALT > 3 times upper limit of normal
- eGFR < 30 ml/min/1.73m²
- Major hypoglycaemic events

- Renal dysfunction (eGFR < 45 ml/min/1.73m² or reduction in eGFR > 25%)
- LFTs > 2.5 times upper limit of normal
- Hb < 10.0 g/dL and fall > 1.5 g/dL from baseline
- Occurrence of clinically relevant Vitamin B12 deficiency, defined as values < 110pmol/L reported in the lab data recorded in the eCRF
- Acute coronary syndrome

These events will be grouped according to whether they warrant discontinuation of study medication or not. The first three events above (lactic acidosis, ALT and eGFR < 30 ml/min/1.73m²) all warrant discontinuation of study medication.

The number and percentage of events of particular interest will be reported. For the events warranting discontinuation of study medication, the number of events occurring whilst taking study medication will be summarised along with these number of events that resulted in discontinuation.

The number and percentage of subjects experiencing at least one event for any and each specific event will also be summarised.

No formal statistical testing will be applied.

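### For an on-study eGFR below 45, Protocol Section 8 makes dose reduction discretionary in one place and directed and permanent in another, and nothing says which governs.

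*Protocol*

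**What the plan says.** Both instructions are current text in Protocol Section 8 and share one trigger, an eGFR below 45 mL/min/1.73 m² during participation.

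- **Choice of eGFR threshold.** After the background on metformin in renal impairment, the protocol sets the entry cut-off at 45 and turns to what happens on study. Below 45, "consideration will be given to IMP dose reduction". Below 30, "IMP will be discontinued".
- **Dose reduction of treatment.** A few paragraphs later, for a value below 45: "on any measurement Investigators should permanently reduce metformin dose to 500 mg twice daily".

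Three other places use the same eGFR levels:

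- **Withdrawal of treatment** (Protocol Section 8) lists "renal impairment with eGFR <30 mL/min/1.73m² during study – see page 28".
- **Abnormal laboratory findings** (Protocol Section 8) requires adverse-event recording of "Reduction in eGFR to < 45 ml/min/1.73 m² and < 30 ml/min/1.73 m²".
- **SAP 2.4.5.4** lists "Renal dysfunction (eGFR < 45 ml/min/1.73m² or reduction in eGFR > 25" per cent) among the events of particular interest, outside the three events that it says warrant stopping study medication.

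**The concern.** The rule is there to protect participants: Section 8 notes that metformin is cleared by the kidney and may accumulate when renal function is poor. The protocol plans for 18 sites in five countries (Section 6g). If some sites work from the threshold text and others from the dose-reduction paragraph, two participants with the same result can be handled differently, with each site able to point to protocol text in support.

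Two reporting steps also depend on the answer. SAP 2.2 summarises and lists protocol deviations, and it is unclear whether an unreduced dose after a value below 45 counts as one. SAP 2.4.5.1 summarises down-titrations and their reasons by treatment group, and those counts would combine sites that reduce on any value with sites that decide case by case.

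**Working it through.** No figure in the plan depends on this point, so the check compares the texts.

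**Step 1. The two instructions side by side.**

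| Feature | Choice of eGFR threshold | Dose reduction of treatment |
|---|---|---|
| Trigger | On-study eGFR below 45 | On-study eGFR below 45 |
| Force | To be considered | Directed |
| Values needed | Not stated | Any measurement |
| Duration | Not stated | Permanent |
| Size of reduction | Not stated | A named dose |
| Object | IMP | Metformin |

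The trigger is the same. The action differs in force, and the second text fixes three things that the first leaves open.

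**Step 2. Responses to one value below 45, tested against each text.**

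| Response | Threshold text | Dose-reduction text |
|---|---|---|
| Considers, then reduces permanently to the named dose | Complies | Complies |
| Considers, then keeps the dose | Complies | Departs |
| Considers, reduces, later restores the dose | Complies | Departs (not permanent) |
| Considers, repeats the test, keeps the dose because the repeat is 45 or above | Complies | Departs (any measurement suffices) |

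The two texts are compatible in the first row only. In the other three, the same conduct is within the protocol on one reading and outside it on the other.

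**Step 3. Does anything else settle it?**

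- The guideline background in the threshold text says "Furthermore the guideline recommends that the dose of metformin be reviewed if the serum creatinine exceeds 130 micromol/L" and gives eGFR below 45 as the alternative trigger. Review is closer to the discretionary wording, but this reports outside guidance and is not an instruction to sites.
- The adverse-event list requires recording at both levels and attaches no dose action.
- The withdrawal paragraph refers back to the threshold text for the below-30 rule. The dose-reduction paragraph has no such reference for below 45.
- SAP 2.4.5.4 treats a value below 45 as an event to report, with no dose rule. SAP 2.4.5.1 counts down-titrations without saying when one is due.

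Nothing in either document ranks one instruction above the other.

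**Step 4. How far does the conflict reach?** For eGFR below 30, the threshold text, the withdrawal paragraph and SAP 2.4.5.4 all call for study medication to stop. The inconsistency is therefore limited to the below-45 tier. The sample size inputs (SAP 1.4) and the primary model (SAP 2.4.1) do not use the dosing rule.

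**The case against.** The strongest reply is that this is loose drafting rather than a contradiction. An investigator who considers a reduction and then makes it as directed satisfies both texts. The discretionary sentence sits in a rationale paragraph, whereas the directive sits among the operational rules on interruption, withdrawal and dose reduction, where a site would look for an action. The specific instruction could be read as completing the general one. Its verb is *should*, while the withdrawal paragraph uses *will*.

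Part of this stands. The texts can be followed together, so it would be wrong to say that they never can. But the discretionary sentence is an on-study instruction, in the same paragraph as the below-30 stopping rule that the withdrawal list relies on, so it cannot be set aside as background. The softer verb does not restore case-by-case judgement when the sentence also specifies any measurement and a permanent change.

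The reply is also right that the analytical reach is small. SAP 1.6.2 analyses all randomised participants with sufficient data regardless of adherence, SAP 2.4.5.1 tests only permanent withdrawals, and the per-protocol definition in SAP 2.1 does not mention dose reduction.

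A reader might infer more in four directions, none of which the documents support:

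- **Unequal handling of the arms.** One text says IMP and the other metformin, but Section 8 defines the IMP as metformin or matching placebo in matching packs. A blinded investigator can only reduce the tablets that the participant has. The wording needs tidying; it is not evidence of different handling.
- **An effect on eGFR as a secondary outcome.** The documents show no mechanism or size for this. Randomisation is stratified by site (Protocol 14.1), so differences in site practice should fall roughly evenly across the arms.
- **A high frequency.** Entry is permitted at an eGFR of 45 or above, but neither document gives a baseline eGFR distribution or within-person variability.
- **A need to recode the SAP.** A recorded reason of eGFR below 45 is the same under either text.

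**Conclusion.** The inconsistency is real and the two texts must be reconciled. For one trigger, Section 8 gives a discretionary instruction and a directed, permanent one. They diverge whenever an investigator considers a reduction and does not make it, or does not make it permanent. Nothing in the protocol or SAP resolves this.

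The consequences are possible differences in dosing between sites for the same result, undefined deviation status for an unreduced dose, and a by-arm down-titration summary without a single meaning. Their size cannot be calculated from the documents. A reader might take the whole renal safety rule to be contradictory, but the below-30 discontinuation rule is consistent, and falls below 45 are recorded and reported whichever text a site follows.

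The conclusion assumes that no site instruction outside the two documents already fixes the rule. If one does, the protocol text still needs to match it.

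**What to change.** Replace the two statements in Protocol Section 8 with one rule for on-study eGFR below 45, and have the other place refer to it. The rule should state:

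1. whether reduction is optional or required;
2. whether a single value is enough;
3. whether the reduction is permanent;
4. that it applies to study medication, using that term in place of metformin.

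The choice among these is a clinical matter for the sponsor and investigators. Once the rule is set, the deviation status of an unreduced dose under SAP 2.2 follows from it, and the summary in SAP 2.4.5.1 can be read against it without changing the SAP.

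The cost is a protocol wording change, handled under Protocol Section 17, and a note to sites. No analysis, sample size or data collection changes.

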- Lactic acidosis (blood pH <7.35 with plasma lactate >5.0 mmol/L): This condition has been associated with metformin, usually in cases of acute renal failure, but there remains no evidence that metformin causes lactic acidosis in stable individuals with adequate renal function.^{23,24} The reported incidence of lactic acidosis in patients receiving metformin hydrochloride is very low (approximately 0.03 cases/1000 patient-years, with approximately 0.015 fatal cases/1000 patient-years) and in 8.4 vs 9.0 cases per 100,000 patient years MF vs other diabetes medications of placebo (www.ahrq.gov – Johns Hopkins). In more than 20,000 patient-years exposure to metformin in clinical trials, there were no reports of lactic acidosis. Risk factors are significant renal insufficiency, liver dysfunction, severe acute congestive heart failure and any state where there is risk of hypoperfusion and hypoxaemia.
- Hypoglycaemia: metformin without concomitant diabetes medications has not been shown to cause hypoglycaemia. However, in combination with insulin therapy, there may be a small additional risk, although neither minor or major overall hypoglycaemia risk was statistically elevated in the largest previous trial.¹⁸ Participants will be informed of the symptoms of hypoglycaemia, namely skin pallor, trembling, perspiration, a feeling of weakness and/or hunger, blurred vision and advised to take appropriate corrective measures e.g. sugar-containing drink or food.
- Pregnancy and lactation: metformin is increasingly considered safe in pregnancy²⁵ but will be an exclusion criterion in this study [see Section 7.3(c)].
- Renal dysfunction: Metformin is excreted renally and may therefore accumulate during significant renal dysfunction. Therefore renal function will be assessed by regular U&E analyses during the trial. Intravascular administration of iodinated contrast agents in particular (e.g. coronary or peripheral angiograms, contrast imaging such as CT scans) may precipitate renal failure with resultant accumulation of metformin. Therefore standard procedures will be followed in such circumstances: the study drug will be discontinued prior to the test and not reinstated until >48 hours later only after it has been verified that renal function has returned to pretest levels.

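### After intravascular iodinated contrast, one part of Protocol Section 8 makes renal recovery a condition of restarting study drug; the interruption list leaves that condition out

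*Protocol*

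**What the plan says.** All the relevant text is in Protocol Section 8 (Medications), in three places.

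- **Risks of treatment, renal dysfunction.** The protocol explains that metformin is cleared by the kidney, and that intravascular iodinated contrast can bring on renal failure and so cause the drug to accumulate. It then instructs that "the study drug will be discontinued prior to the test and not reinstated until >48 hours later", and "only after it has been verified that renal function has returned to pretest levels".
- **Interruption of treatment.** One item in the list is "Requirement for investigation involving intravascular iodine-containing contrast agent (as per national guidelines"; for it, "treatment will be discontinued 48 hours prior to investigation and recommenced no earlier than 48 hours afterwards". The item ends there. The item just above it, on elective surgery under general anaesthesia, uses the same 48-hour intervals before and after and adds that drug is resumed "only when it has been confirmed that renal function has returned to pre-operative levels".
- **The paragraph after the list.** For all the listed interruptions, "treatment will be restarted where possible in accordance with the Investigator's clinical judgement, local practice, standard-of-care, and national guidelines".

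Neither contrast text refers to the other on this point.

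**The concern.** The two contrast texts cover the same situation but do not give the same conditions for restart. Under Risks of treatment, elapsed time is not enough: renal function must also be shown to have recovered. In the interruption list, only elapsed time is stated. Because the surgery item spells out a renal condition and the contrast item next to it does not, someone using the list on its own could take the difference as deliberate.

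What is at stake is participant safety. The hazard is one that the protocol itself describes: renal function worsens after contrast, and a renally cleared drug is then resumed. A second, smaller consequence is that sites could handle the same event differently according to which text they consult.

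**Working it through.** No figure in the plan depends on this point, so there is nothing to recompute. The check sets the two texts side by side, element by element.

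| Element | Risks of treatment (renal dysfunction) | Interruption of treatment (contrast item) | Comparison |
|---|---|---|---|
| Situation | Intravascular iodinated contrast | The same, qualified by reference to national guidelines | Same scope |
| Stop time | Before the test, no interval given | 48 hours before | Differs in precision only |
| Minimum wait | More than 48 hours | At least 48 hours | Effectively the same |
| Renal condition for restart | Required | Not stated | Inconsistent |

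**Stop time.** Stopping 48 hours before the test is also stopping before the test, so one action satisfies both texts. A site reading only the risk text would lack the interval, but the two do not conflict.

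**Minimum wait.** If the wait in the risk text is counted from the test, which is its natural reading, the two rules differ only at exactly 48 hours. That has no practical consequence.

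**Renal condition.** Take a participant at, say, 72 hours after contrast whose renal function has not been rechecked, or has been rechecked and is still below its pretest level. The time condition is met under both texts (72 is greater than 48). Under Risks of treatment, restart is not allowed. Under the contrast item, no stated condition is unmet. This is the one element on which the texts lead to different actions.

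**Does another provision close the gap?**

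1. The general restart rule after the list relies on investigator judgement, local practice, standard of care and national guidelines. It states no renal check. The trial runs in five countries (Protocol Section 6(g)), and the content of their guidelines is not in the documents, so a uniform check cannot be assumed.
2. The renal thresholds elsewhere in Section 8 (a dose rule below an eGFR of 45 and withdrawal below 30, both in ml/min/1.73 m²) act only once a value has been obtained. They are also absolute thresholds, whereas the risk text requires return to the participant's own pretest level. A fall from, for example, 85 to 60 would cross neither threshold and would still not be a return to pretest level.
3. In the Schedule of Assessments, U&E after randomisation is due at months 3, 6, 12, 18, 24, 30 and 36. No scheduled sample is tied to the days after a contrast procedure.
4. The advice under Unblinding to stop study medication during hospitalisation with acute illness concerns stopping, not the conditions for restart.

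None of these supplies the missing condition.

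**The case against.** The strongest reply is that the protocol already contains the safeguard. The risk text is in the same section and is worded as an instruction. Nothing in the documents ranks the interruption list above it. The contrast item sets a minimum wait; it does not say that the wait is sufficient or that a renal check is unnecessary. Read together, the two texts are compatible, and following both includes the check. The reference to national guidelines and the general restart rule also mean that restart is not automatic at 48 hours.

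Much of this stands. It limits the point to an omission and rules out two stronger readings that a reader might infer:

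- **That the texts disagree on when to stop drug or how long to wait.** They do not. One stop time is less specific than the other, and the waits are effectively equal.
- **That the interruption list waives the renal check after contrast.** It does not say so. The contrast with the surgery item makes that inference easy, but it remains an inference.

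What the reply does not remove is that one of the two places where a site would look for the rule leaves out a condition that the other makes mandatory, with no cross-reference. Compliance then depends on the site having read both.

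It is also fair to say that exposure is unquantified. Exclusion of recent acute coronary syndrome, stroke or TIA, and of angina on mild or moderate exertion, lowers the near-term need for angiography. Against that, known cardiovascular or peripheral vascular disease counts towards eligibility, entry is open down to an eGFR of 45, and coronary and peripheral revascularisation are listed adverse events of medical interest. Contrast procedures over three years are foreseeable, but their number cannot be derived from the documents.

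**Conclusion.** The point holds in a narrow form. Section 8 makes demonstrated renal recovery a condition of restart after contrast in one place and omits it from the interruption list, and no other provision fills the gap. It is an internal inconsistency with a bearing on participant safety, not a flaw in the design or the analysis: the primary endpoint, sample size, power and type I error are untouched.

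The conclusion rests on two assumptions: that some staff will consult the interruption list without the risk text, and that the reference to national guidelines does not by itself guarantee a renal check at every site. Neither can be tested from the documents. No position is taken on which clinical rule is right.

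**What to change.** Reconcile the two contrast texts in Section 8 into a single instruction that states the stop time, the wait and whether a renal condition applies to restart. Put it in one place and cross-refer from the other. In the same edit, make clear how the general restart rule after the list relates to any condition stated in an individual item. The content of the rule is a clinical decision for the sponsor and its advisers.

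The cost is small: a wording change handled under Protocol Section 17, with the sponsor judging whether it is substantial and so needs regulatory and ethics submission, plus a short note to sites. No change to the SAP, the database or the sample size is needed.
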